Describe the provisions included in the research to protect the privacy interests of participants (e.g., others will not overhear your conversation with potential participants, individuals will not be publicly identified or embarrassed).

All discussions with potential participants will be done in clinic rooms with the door closed so others will not be able to overhear the conversation. Potential participants will in no way be publicly identified or embarrassed.

22. Procedures to Maintain Confidentiality

a. Describe the manner and method for storing research data and maintaining confidentiality. If data will be stored electronically anywhere other than a server maintained centrally by UAB, identify the departmental and all computer systems used to store protocol-related data, and describe how access to that data will be limited to those with a need to know.

The study database will be maintained on a computer with access restricted by password protection to study staff. A non-specific participant number will be generated for each participant (e.g., CKD1501). The list linking the participant numbers to the participant identifiers will kept in a secure location with password-protection, and only the PI and designated study personnel will have access to this list. Data will be stored with use of the participant numbers without identifiable labels such as names, medical record number or social security number.

- b. Will any information derived from this study be given to any person, including the subject, or any group, including coordinating centers and sponsors? Xes No
 If Yes, complete i-iii.
 - i. To whom will the information be given? UAB IRB
 - **ii.** What is the nature of the information? Summary data without individual personal identifiers
 - **iii.** How will the information be identified, coded, etc.? Information will only be presented as summarized data without individualized information.

23. Additional Information

In the space below, provide any additional information that you believe may help the IRB review the proposed research, or enter "None." \underline{None}

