Study participants with proteinuric, CKD will be randomly assigned in a double-masked fashion to spironolactone 25mg daily or amiloride 5 mg daily for 6 weeks and then crossed over to the alternate study medication after a 1 month wash-out period (See Figure 1). Vascular function will be assessed at baseline and the end of each 6 week treatment period by: 1) ultrasound guided flowmediated dilation (FMD) of the brachial artery, 2) impedence cardiography, 3) pulse-wave velocity, 4) 24 hour ambulatory blood pressure monitoring, and 5) serum and urine biomarkers. Participants will undergo a total of 7 visits over 16-18 weeks; 3 of the 7 visits will involve vascular function testing.

Pulse-wave velocity is measured non-invasively with placement of a small sensor (tonometry probe) over the carotid and femoral artery. This procedure poses no discomfort and is usually done in about 15 minutes. Impedence cardiography is also noninvasive with minimal inconvenience to the participant. It is performed by placing small electrode pads on the chest wall and neck and takes about 12 minutes. FMD is measured by assessing the change in brachial artery diameter by ultrasound. A blood pressure cuff is placed below the elbow and inflated above systolic blood pressure for 5 minutes. The cuff is then released and change in brachial artery is determined immediately afterwards for 2 minutes. The entire procedure takes about 45 minutes. Some back discomfort can occur with FMD testing as participants must lie flat for 30 minutes. Hand and arm discomfort from cuff inflation is common yet resolves immediately after cuff deflation. Collection of urine for 24 hours and wearing a blood pressure monitor for 24 hours can be disruptive to normal daily/nightly activities; however poses no danger or long-term inconvenience.

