A study visit where vascular function testing is to be performed will begin at 0800 in the morning and start with a vital sign assessment including height, weight, body fat percent, and left arm automated BP measurement followed by confirmation of fasting status and a brief past medical history. Each participant will then lie supine for 10 minutes in preparation for vascular function testing. Following the pulse wave velocity, impedence cardiography, and FMD measurements, the participant will have his/her blood and urine collected for laboratory testing. Laboratory testing will include ~20 mL of blood for plasma and serum testing. Participants will return 24 hour urine samples and have a 24 hour ambulatory monitor placed. This entire visit is expected to take 2 hours.

Study visits where vascular function testing will not be performed (e.g., screening visit, visit 2, visit 4, and visit 5; see Table 2) should last 30 minutes and involve a medication assessment, vital sign check, and blood collection for serum potassium (~4 mL).

All study medication will be prepared by the UAB Research Pharmacy in matching capsules.. The order of medication dispensing will follow simple randomization using an *a priori* randomization list prepared by the research pharmacy.

[figure not shown]

Figure 1: Study design

VFT = vascular function testing (i.e., ultrasound assessed flow-mediated dilation and biomarker measurement), 24hrU = 24 hour urine collection, 24hrABPM = 24 hour ambulatory blood pressure monitoring, K = potassium *30-60 mL/min/1.73m² eGFR by MDRD, proteinuria defined as ACR \geq 30 mg/g

- b. What is the probable length of time required for the entire study (i.e., recruitment through data analysis to study closure)?
 5 years
- **c.** What is the total amount of time each participant will be involved? 16 weeks

- **d.** If different phases are involved, what is the duration of each phase in which the participants will be involved? If no phases are involved, enter "not applicable." The cross-over design consists of two 6 week intervention periods separated by a one month washout period.
- **e.** List the procedures, the length of time each will take, and the frequency of repetition, and indicate whether each is done solely for research or would already be performed for treatment or diagnostic purposes (routine care) for the population. *Insert additional table rows as needed.*

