Table 2. Combined study procedure schedule								
	Screen Visit	Visit 1	Visit 2	Visit 3	Visit 4	Visit 5	Visit 6	
	Week -(1-2)	Week 0	Week 2	Week 6	Week 10	Week 12	Week 16	
Informed consent	Х							
Study medication pill count			Х	Х		Х	Х	
Con medication assessment		Х		Х	Х		Х	
Dispense study medication		Х			Х			
Clinic vital signs	Х	Х	Х	Х	Х	Х	Х	
FMD		Х		Х			X	
ACR	Х	Х		Х			X	
RFP	Х			Х			X	
24 hour ABPM		Х		Х			Х	
Plasma aldosterone, PRA		Х		Х			Х	
Blood & urine biomarkers*		Х		Х			Х	
Serum potassium via BMP			Х		Х	Х		
24hr urine collection		Х		Х			Х	
Urine Pregnancy Test	Х							
Con = concomitant, FMD = flow-mediated dilation, ACR = spot urinary albumin-to-creatinine ratio, RFP = renal function panel, PRA = plasma renin activity, BMP = basic metabolic panel, ABPM = ambulatory blood pressure monitor *Biomarkers include serum high-sensitivity C-reactive protein (hsCRP), serum pentraxin-3 (PTX-3), serum fetuin-A, serum uric acid, plasma asymmetric dimethylarginine (ADMA), serum soluable vascular cell adhesion molecule (sVCAM-1), homeostasis model assessment method of insulin resistance (HOMA-IR), plasma and urine F2-								
isoprostanes, and plasma endothelin.								

All procedures will be for research purposes. Study visits 1, 3, and 6 will be approximately 120 minutes in length. Study visits 2, 4, and 5 will be approximately 30 minutes in length.

- **f.** Will an interview script or questionnaire be used? □Yes ⊠No **If Yes**, attach a copy.
- **g.** Will participants incur any costs as a result of their participation? **If Yes**, describe the reason for and amount of each foreseeable cost.
- **h.** Will participants be compensated?

If Yes, complete i-v:

i. Type: (e.g., cash, check, gift card, merchandise): Check

ii. Amount or Value: \$100 for the study visits 1, 3, and 6 and \$50 for study visits 2, 4, 5, screening visit, and unscheduled visit(s).

iii. Method (e.g., mail, at visit): Mail

iv. Timing of Payments: (e.g., every visit, each month): After the visit

v. Maximum Amount of Payments per Participant: \$500 (not including any unscheduled visits)

🔄 Yes 🖂 No

Yes No

17. Describe the potential benefits of the research.

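### Does fitting the 24-hour blood pressure monitor at Visits 1, 3 and 6 put the recordings on the wrong side of the treatment boundary?

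*Protocol*

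**What the plan says.** Section 16.a lists five vascular assessments, the fourth being 24-hour ambulatory blood pressure monitoring (ABPM), and states when they are meant to be taken: "Vascular function will be assessed at baseline and the end of each 6 week treatment period by". Each participant is assigned "to spironolactone 25mg daily or amiloride 5 mg daily for 6 weeks" and then crosses over. Section 16.d gives the structure: "The cross-over design consists of two 6 week intervention periods separated by a one month washout period".

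On the visit itself, Section 16.a says: "A study visit where vascular function testing is to be performed will begin at 0800 in the morning", and "This entire visit is expected to take 2 hours". On urine and ABPM it says: "Participants will return 24 hour urine samples and have a 24 hour ambulatory monitor placed".

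Table 2 in Section 16.e ticks ABPM at Visit 1 (week 0), Visit 3 (week 6) and Visit 6 (week 16). The row "Dispense study medication" is ticked at Visits 1 and 4 (weeks 0 and 10). The row "Study medication pill count" is ticked at Visits 2, 3, 5 and 6.

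The supplied text does not state when the first or last capsule of a period is taken, or whether capsules are taken while a monitor is worn. Figure 1, whose legend includes ABPM, is not shown.

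**The concern.** The urine collection looks back from the visit and the monitor looks forward. Read against the nominal weeks, the Visit 1 recording lies in the first day of weeks 0 to 6, the Visit 3 recording in the first day of the washout, and the Visit 6 recording after week 16. If capsules start on the dispensing day and stop the day before the closing visit, the baseline is partly treated and the end-of-period recordings are taken after dosing has ceased.

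Both errors would shrink the measured change in blood pressure from baseline. If a fraction r of the effect were lost, the sample size needed to hold power would grow by 1/(1 − r)². The contrast between the two drugs could also pick up any difference in how quickly their effects fade. Flow-mediated dilation, blood and urine are collected at or before the visit and would not be affected in the same way.

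**Working it through.** **Inputs.** From Sections 16.a, 16.d and 16.e: visits at weeks 0, 6, 10 and 16; daily dosing for six weeks per period; visit start 08:00; visit length 2 hours. Assumed, because the text is silent: the monitor goes on at about 08:00 + 2 h = 10:00 and comes off 24 hours later; 42 capsules per period; first capsule on the dispensing day or the day after.

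**The plan's own timeline.** 6 + 4 + 6 = 16 weeks, which matches Section 16.c. Screening one to two weeks earlier gives 17 to 18 weeks, within the 16 to 18 stated in Section 16.a. In days, Visits 1, 3, 4 and 6 fall on days 0, 42, 70 and 112.

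**Recording windows.** Visit 1: day 0, 10:00, to day 1, 10:00. Visit 3: day 42, 10:00, to day 43, 10:00. Visit 6: day 112, 10:00, to day 113, 10:00.

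**Exposure under different capsule times.** In period 1 the 42nd capsule falls 41 days after the first. Period 2 gives the same end-of-period results, shifted by 70 days.

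| First capsule | Baseline hours after first capsule | 42nd capsule | Visit 3 recording relative to capsules |
|---|---|---|---|
| Day 0, 12:00 | 22 of 24 | Day 41, 12:00 | 22 to 46 h after the last capsule |
| Day 0, 20:00 | 14 of 24 | Day 41, 20:00 | 14 to 38 h after the last capsule |
| Day 1, 08:00 | 2 of 24 | Day 42, 08:00 | 2 to 26 h after the last capsule |
| Day 1, 12:00 | 0 of 24 | Day 42, 12:00 | last capsule taken 2 h into the recording |

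A one-day shift with the same number of capsules removes the problem or nearly so. In the evening case, 24 − 14 = 10 of the 24 recorded hours still lie within one normal dosing interval. All four rows are compatible with the supplied text.

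**Does the text select the unfavourable row?** Dispensing records hand-out, not ingestion. A pill count is not an instruction to stop: the same row is ticked at Visits 2 and 5, in mid-period, when dosing continues. Table 2 has no row that ends dosing. The only stated intent is that ABPM be measured at baseline and at the end of treatment.

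**Effect on the comparison between drugs.** For one participant, (Visit 3 − Visit 1) − (Visit 6 − Visit 1) = Visit 3 − Visit 6. The baseline recording cancels. The end-of-period lag is the same at Visits 3 and 6 and in both sequences. With effects S and A and a common loss r, the contrast becomes (1 − r)(S − A): attenuated, but not tilted towards either drug. A spurious difference requires unequal losses, and the protocol gives no figure for either.

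**Sample-size factor.** 1/(1 − 0.25)² = 1.78 and 1/(1 − 0.50)² = 4.0. The arithmetic is right, but 25% and 50% are assumptions with no source in the protocol, and the supplied text does not say that the 62 participants were sized on ABPM. These factors illustrate the formula; they do not estimate a loss in this trial.

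**The case for a change.** The strongest case for acting is that the schedule cannot guarantee what Section 16.a intends. Participants could follow different rows of the table above and all comply. The counts at Visits 3 and 6 take place at the visit where the monitor goes on, Visit 4 has no count and no visit follows Visit 6, so no scheduled count shows whether a capsule was taken during the recording. Visit 4 has no ABPM, so Visit 1 is the only untreated reference. An analyst cannot recover a dose time that was never recorded.

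Most of that is correct as a description. It shows a detail left unstated, not a contradiction or a wrong statement. Staff who are told to obtain a baseline and an end-of-treatment recording have an obvious way to read the instruction. Dosing detail may also sit in Figure 1 or in the Drug Review Sheet that Sections 7 and 19 call for, neither of which is in the supplied text.

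Nor is the alternative free. Recording before the closing visits needs an earlier contact to fit the monitor, and the nearest scheduled ones are four weeks before (week 2 for week 6, week 12 for week 16). Fitting at screening would separate the baseline ABPM from the other baseline measures by one to two weeks. Counting pills at monitor removal may need attendance the day after the visit, which Table 2 does not contain. Redefining when a period starts or ends would alter treatment timing to settle a question of at most about a day.

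**Conclusion.** The observation about direction is correct: urine looks back from the visit, ABPM looks forward, and by nominal weeks the recordings sit just past the boundaries. The inference that the baseline is therefore treated and the end recordings untreated is not supported, because no capsule times are given and a one-day difference in the first capsule reverses the result.

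At worst, under the assumptions of 42 capsules and a monitor running from about 10:00, the misalignment is about one dosing day in 42. It bears mainly on change from baseline in one of five assessments, and much less on the spironolactone–amiloride contrast, where timing is common to both drugs and the baseline drops out. Its effect on blood pressure cannot be sized from the document.

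This is a gap that staff would fill sensibly in line with the stated intent. Noting capsule times around each recording would be ordinary good practice, but the plan needs no change on this point.

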Chronic kidney disease, an inpairment in kidney function beyond age-expected decline, is commonly attributed to kidney damage from diabetes mellitus and/or hypertension. While the direct mechanism(s) of kidney injury resulting from these comorbidities has yet to be defined, it has been hypothesized that the vasculature is involved in kidney function. This hypothesis is supported by the evidence that the one proven therapy for chronic kidney disease, namely angiotensin converting enzyme inhibitors (ACEIs) or angiotensin receptor blockers (ARBs), improves vascular function.

In our study of patients with resistant hypertension, we have shown that vascular function improves with the use of spironolactone, a mineralocorticoid receptor antagonist. Spironolactone has also been shown to reduce urinary protein loss in patients with chronic kidney disease. Therefore, it is reasonable to suppose that spironolactone can improve vascular function in patients with chronic kidney disease. Currently spironolactone is used sparingly in early stages of chronic kidney disease and is avoided in late stages of chronic kidney disease due to the risk of raising serum potassium levels. If spironolactone improves vascular function in patients with moderate stages of chronic kidney disease, as it has been shown to do in patients with resistant hypertension, then defining this mechanism would open new therapeutic avenues for patients with chronic kidney disease.

15. Participants (Screening and Selection)

a. How many participants are to be enrolled at UAB? 62 If multi-center study, total number at all centers:

b. Sex: 50% Male

Race/Ethnicity: All races and ethnicities in the Birmingham area will be enrolled. Enrollment is expected to be composed of 65% African American (chronic kidney disease is more prevalent among African Americans).

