Exclusion Criteria	 Severe HTN (office BP ≥ 160/100 mm Hg) Hypotension (office BP < 110/70 mm Hg) Serum potassium > 5 mEq/L History of arrhythmia, including atrial fibrillation Pregnant or breast feeding woman DM type 1 DM type 2 with hemoglobin A1C ≥ 6.5 % Dementia or cognitive impairment prohibiting informed consent History of ischemic stroke, unstable angina, or myocardial infarction within the past 6 months Allergy or intolerance to spironolactone or amiloride Use of an MR antagonist or an epithelial sodium channel blocking medication within the last month 				

Describe the inclusion/exclusion criteria:

ACR = albumin-to-creatinine ratio, HTN = hypertension, BP = blood pressure, DM = diabetes mellitus, MR = mineralocorticoid receptor

Patients with severe hypertension (office BP > 160/100 mm Hg) are excluded due to 1) the possibility of requiring blood pressure medication changes during the study period, 2) direct effects of blood pressure on vascular function testing, and 3) increased cardiovascular risk leading to potential serious adverse events. Patients with hypotension (office BP < 110/70 mm Hg) were excluded due to an expected drop in blood pressure with administration of spironolactone and/or amiloride.

- d. If participants will comprise more than one group or stratification, describe each group (e.g., treatment/intervention, placebo, controls, sham treatment) and provide the number of participants anticipated in each group.
 This clinical trial follows a cross-over design. All participants are scheduled to receive both study medications in series with randomization to the initiating therapy (See Figure 2).
- e. Indicate which, if any, of the special populations listed below will be involved in the protocol. Include the Special Populations Review Form (SPRF) if indicated.
 Pregnant Women: Attach SPRF—Pregnant Women, Fetuses,
 - Neonates/Nonviable Neonates
 - Fetuses: Attach SPRF—Pregnant Women, Fetuses, Neonates/Nonviable Neonates
 - Neonates/Nonviable Neonates: SPRF—Pregnant Women, Fetuses, Neonates/Nonviable Neonates
 - Prisoners: Attach SPRF—Prisoners
 - Minors (<19 years old): Attach SPRF—Minors
 - Employees or students at institution where research conducted
 - Persons who are temporarily decisionally impaired

Persons who are permanently decisionally impaired (e.g., mentally retarded)
Non-English Speakers

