There is no anticipated direct benefit which the participants will obtain from participating in the protocol. However, indirect benefits may include discovering that spironolactone or amiloride reduces albuminuria and/or blood pressure. In addition, participants who experience an improvement in endothelial function with spironolactone use would be expected to have a lower cardiovascular risk with continued use. We feel the risks involved with participating in this study are reasonable in relation to the potential benefits.

18. Risks

- a. List the known risks—physical, psychological, social, economic, and/or legal—that participants may encounter as a result of procedures required in this protocol. Do not list risks resulting from standard-of-care procedures. Note. Risks included in this protocol document should be included in the written consent document. No undue hazards (physical, psychological, financial, legal, or other) are anticipated with vascular function testing or blood and urine sampling. Participants may be exposed to several potential risks as itemized below:
 - 1. Hyperkalemia: Administration of both spironolactone and amiloride are associated with increases in serum potassium of approximately 0.4 mEq/L. Serum levels of potassium will be monitored at each study visit. Kayexalate and a low potassium diet will be administered for levels of serum potassium > 5.5 meq/L followed by a repeat potassium level in 3 days. Participants will be withdrawn from the study with serum potassium levels > 6.0 meq/L. In addition, participants will not be allowed to participate in the second treatment period with a serum potassium > 5.0 meq/L when checked at week 10.
 - 2. Fetal toxicity: Spironolactone is associated with fetal toxicity. Pregnant women, as determined by a screening urine sample, are excluded from study participation. Women of child bearing potential will be advised of the risk of fetal toxicity, and if a pregnancy occurs during the study the participant will be withdrawn and study medication stopped.
 - 3. Gynecomastia: Spironolactone is associated with breast growth in men. This association occurs more frequently with the long-term use of doses exceeding 50mg/day.
 - 4. Discomfort and risks (hematoma/skin infection) associated venous blood collection

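### Simple randomization of drug order leaves the sequence split of a 62-person crossover to chance; a permuted-block list would nearly remove this small, avoidable loss of precision

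*Protocol*

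**What the plan says.** Item 15.d describes the crossover: "All participants are scheduled to receive both study medications in series with randomization to the initiating therapy". Item 16.d gives its shape: "The cross-over design consists of two 6 week intervention periods separated by a one month washout period". The planned number is in item 15.a: "How many participants are to be enrolled at UAB? 62".

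Item 16.a fixes the assignment method: "The order of medication dispensing will follow simple randomization using an" advance "randomization list prepared by the research pharmacy". The same item makes the trial double-masked and adds "All study medication will be prepared by the UAB Research Pharmacy in matching capsules".

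The Protocol mentions no blocking, stratification or other control of how many people start on each drug. It does not state the allocation ratio, and it gives no power, significance level, effect size, standard deviation or period effect.

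**The concern.** In a two-treatment, two-period crossover with period in the model, the treatment effect is estimated by comparing period differences between the two sequences. It is most precise when the sequences are equal in size. Simple randomization leaves that balance to chance, so some precision can be lost for no gain. A later analysis plan cannot rebalance sequences that have already been allocated.

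Two things are at stake, both limited:

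- With period modelled, an uneven split costs some power and causes no bias.
- If period were not modelled, the plain mean of spironolactone minus amiloride would carry part of any period effect, in proportion to the imbalance that happened to occur. The analysis is not shown, so this second point is conditional.

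**Working it through.** **Inputs.** From the Protocol: N = 62 (item 15.a), two sequences (item 15.d), simple randomization (item 16.a). Assumed, because the Protocol does not give them: probability 1/2 for each sequence, all 62 allocated and analysed, two-sided 5% test, 80% power at 31:31. There is no stated figure to reproduce.

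**1. How uneven the split can be.** With n1 ~ Binomial(62, 0.5):

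- 26:36 or worse: 2 × P(n1 ≤ 26) = 0.253
- 24:38 or worse: 2 × P(n1 ≤ 24) = 0.098

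**2. Efficiency.** With period modelled, the variance of the treatment effect is proportional to 1/n1 + 1/n2. Relative to an equal split, efficiency is 4·n1·n2/N², with N² = 3844. The equivalent loss in participants is 62 × (1 − efficiency).

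**3. Power.** The test has 62 − 2 = 60 degrees of freedom. A noncentrality of 2.847 gives 80% at 31:31, which is an effect of 2.847/√62 = 0.362 SD of the within-person difference. At other splits the noncentrality is 2.847 × √efficiency.

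| Split | Efficiency | Participants lost | Power |
|---|---|---|---|
| 31:31 | 1.0000 | 0 | 80.0% |
| 30:32 | 3840/3844 = 0.9990 | 0.1 | 79.96% |
| 26:36 | 3744/3844 = 0.9740 | 1.6 | 79.0% |
| 24:38 | 3648/3844 = 0.9490 | 3.2 | 77.9% |
| Average over simple lists | | 1.0 | 79.3% |

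Starting instead from an assumed 90%, the average is 89.5% and the value at 24:38 is 88.5%.

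**4. With blocks.** Over 20,000 lists of randomly varying blocks of 2, 4 and 6 cut at 62, 81% ended 31:31, 19% ended 30:32, and none was worse.

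**5. If period were not modelled.** The paired mean then carries the period effect multiplied by |n1 − n2|/N: 10/62 = 16% at 26:36, 14/62 = 23% at 24:38, and at most 2/62 = 3% at 30:32. For assumed period effects of 0.1, 0.25 and 0.5 SD of the within-person difference, 200,000 simulated trials per setting gave:

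| Period effect | Type I error, simple lists | Power, simple lists | Power at 31:31 |
|---|---|---|---|
| 0.1 SD | 5.0% | 79.5% | 79.8% |
| 0.25 SD | 4.9% | 77.5% | 78.3% |
| 0.5 SD | 5.0% | 70.8% | 72.9% |

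Over all allocations the error rate is not inflated. At 0.5 SD, omitting period costs about 9 points of the 80%, and balance recovers only about 2 of them. The period term matters more than the blocking.

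**6. Losses after allocation.** With an assumed 9 losses (53 completers) at random, mean imbalance is 4.3% of completers starting from 31:31, against 11.0% under simple randomization. If all 9 fell in one sequence, 31:31 would become 22:31, an imbalance of 9/53 = 17%.

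**7. Allocations already made.** If 30 people had been allocated by simple randomization and the other 32 were then split 16:16, a final split of 26:36 or worse needs 10:20 or worse among the first 30: 2 × P(Binomial(30, 0.5) ≤ 10) = 0.099.

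**The case against.** The strongest reply is that nothing here is wrong. Simple randomization is valid, unbiased over allocations, and the least predictable scheme. About three lists in four (27:35 or better) lose at most 0.7 points of power, and the 24:38 case is roughly one in ten. The 80% base is an assumption, and the analysis may well include a period term. All of this stands, and it is why the point is minor. The main power figures already assume that period is modelled.

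Unpredictability would weigh more if staff could see allocations. With masking, matching capsules and a pharmacy-prepared list, little of it is lost.

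Three further limits also stand:

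- **62 may not be the number allocated.** Item 15.a speaks of enrolment, and Table 2 places consent at the screening visit, before first dispensing. If consented screen failures count, fewer are allocated and the 30:32 bound shifts slightly. At 61 the same blocks can end 29:32, which happened in 1.6% of 20,000 lists. The effect on power is trivial.
- **Blocking balances those allocated, not those who finish.** Under item 18.a "participants will not be allowed to participate in the second treatment period with a serum potassium" above a stated limit at week 10, so the analysed split can still drift. The case of all 9 losses in one sequence is a bound and not a forecast: item 18.a gives both drugs the same approximate potassium rise.
- **Some allocations may already have been made.** Item 15.g adds a records search to meet recruitment goals, which may mean that enrolment had begun. The Protocol does not settle this.

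**Conclusion.** The concern holds as a minor, inexpensive improvement. The Protocol fixes a method that is sound but less efficient than one available at almost no cost. The expected gain is about one participant's worth of information, and more than three in about one trial in ten. That is small, but each participant attends 7 visits over 16 to 18 weeks.

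This rests on 1:1 allocation, all 62 being allocated, an assumed 80% power at an equal split, a two-sided 5% test and a period-adjusted analysis. It implies no bias and no inflated type I error. The gain is smaller if many people have already been allocated or if losses differ between sequences.

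**What to change.** In item 16.a, replace simple randomization with a permuted-block list prepared and held by the research pharmacy. Use randomly varying even block sizes (for example 2, 4 and 6) and do not disclose them to study staff. State the 1:1 ratio. Apply the list to allocations not yet made, and keep a period term in the analysis whichever list is used.

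The cost is a new list, a short amendment and slightly less unpredictability, which masking, matching capsules and undisclosed block sizes keep small. No dose, schedule or clinical rule changes.
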